5.1. Summary of Study Design

Study I1F-MC-RHBV is a Phase 3, multicenter, randomized, double-blind, active and placebo-controlled, parallel-group, outpatient study examining the efficacy and safety of ixekizumab treatment regimens (80 mg Q2W and 80 mg Q4W SC), as compared to placebo SC in patients with active rad-axSpA who are biologic DMARD naïve, during a double-blind, 16-week treatment period. Starting doses of 80 mg and 160 mg (at Week 0) will be evaluated for each ixekizumab regimen. Adalimumab (at the approved dosing regimen of 40 mg SC Q2W) has been selected as the active control for comparison with placebo.

Study RHBV will also evaluate long-term efficacy and safety of ixekizumab during the Extended Treatment Period (Period 3) for a total treatment duration of 1 year (52 weeks). Patients that complete Study RHBV may be eligible to enroll into a long-term study (Study I1F-MC-RHBY [RHBY]) for up to 2 additional years. Patients that do not enroll into Study RHBY will complete the Post-Treatment Follow-Up Period (Period 4) in Study RHBV.

[Figure RHBV.5.1](#) illustrates the study design.

Abbreviations: LV = last visit; LY = ixekizumab; n = number; Q2W = every 2 weeks; Q4W = every 4 weeks; SC = subcutaneous; V = study visit; W = study week

- a All patients will receive 3 injections at baseline, as detailed in Protocol Section 6.1. Patients randomized to an ixekizumab regimen will be randomized to a 160 mg starting dose or 80 mg starting dose at a 1:1 ratio (within each ixekizumab regimen).
- b Patients in the adalimumab treatment group will be re-randomized at Week 16 to ixekizumab 80 mg Q4W or Q2W. They will receive their last adalimumab dose at Week 14. There will be a 6-week wash-out period. Patients will receive their first ixekizumab dose at Week 20. Please refer to Protocol Section 6.1 for more details.
- c All patients will receive 2 injections at Week 16, as detailed in Protocol Section 6.1. Patients randomized to placebo at Week 0 will begin ixekizumab 80 mg Q4W or ixekizumab 80 mg Q2W at Week 16 with a 160 mg starting dose (Protocol Section 6.1).
- d Patients who discontinue from study treatment for any reason and who have received at least 1 dose of investigational product will continue to the early termination visit (ETV) before entering the Post-Treatment Follow-Up Period. V801 and V802 are required for all patients; V803 may be needed depending on neutrophil counts (Protocol Section 8.4.10.1).

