5.3. Determination of Sample Size

Approximately 320 patients will be randomized at a 1:1:1:1 ratio in the Blinded Treatment Dosing Period (Period 2) to ixekizumab 80 mg Q2W, ixekizumab 80 mg Q4W, adalimumab 40 mg Q2W, and placebo. With 80 patients per treatment group, this study will have approximately 96% power to test the superiority of ixekizumab Q2W to placebo for the ASAS40 at Week 16. The following assumptions were used for the power calculations for ASAS40 response rates at Week 16 regardless of starting dose: 44% for ixekizumab 80 mg Q2W treatment group and 16% for the placebo group. A 2-sided Fisher's exact test at the 0.05 level is assumed. These assumptions are based on the review of historical clinical studies in rad-axSpA (etanercept, adalimumab, infliximab, certolizumab, and golimumab [Davis et al. 2003; van der Heijde et al. 2005 and 2006; Inman et al. 2008; Landewé et al. 2014]) and recent secukinumab data in patients who are TNF-naïve (Baeten et al. 2014; Sieper et al. 2014).

6. A Priori Statistical Methods

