6.1.1. General Considerations for Analyses during the Blinded Treatment Dosing Period (Period 2)

Comparisons between each ixekizumab regimen (80 mg Q2W or 80 mg Q4W) and placebo, as well as comparisons between adalimumab and placebo, will be performed for all analyses in Period 2.

Period 2 starts at the first injection of study treatment at Week 0 (Visit 2) and ends prior to the first injection of study treatment at Week 16 (Visit 8) or the ETV (between Weeks 0 and 16).

Baseline will be defined as the last available value before the first injection for efficacy, health outcome, and safety analyses. In most cases, this will be the measure recorded at Week 0 (Visit 2). For efficacy measures, if the patient does not take any injection, the last available value on or prior to randomization date will be used. Change from baseline will be calculated as the visit value of interest minus the baseline value. For safety analyses using a baseline period, the baseline period is defined as the time from Visit 1 to the date/time of the first injection.

The randomization to treatment groups is stratified by country and baseline CRP status (nonelevated versus elevated) as described in Section 5.2. The countries will be categorized into geographic regions for analysis. Geographic regions are defined in Section 6.2. Unless otherwise specified, the statistical analysis models will adjust for geographic region and baseline CRP status.

Unless otherwise specified, treatment groups of ixekizumab 80 mg Q2W and Q4W will be analyzed without regard to starting dose.

The primary analysis method for treatment comparisons of categorical efficacy and health outcome variables at specific time points will be made using a logistic regression analysis with treatment, geographic region (Europe and non-Europe), and baseline CRP status in the model using PROC Logistic with a Wald test. The odds ratio and 95% CIs will be reported; treatment difference and 95% CI will also be reported. Secondary analysis will be conducted using a Fisher's exact test. In the case when logistic regression model does not produce statistical results due to sparse data, Fisher's exact test will be used.

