For response rates, starting dose comparisons within ixekizumab Q2W or Q4W treatment regimens will be based on logistic regression model with treatment, starting dose, and treatment-by-starting-dose interaction (only ixekizumab Q2W and Q4W will be included in the analyses). Starting dose comparison combining ixekizumab Q2W and Q4W treatment regimens will be based on logistic regression model with only starting dose in the model.

For mean change analysis, starting dose comparisons within ixekizumab Q2W or Q4W treatment regimens will be based on MMRM model with treatment, starting dose, baseline value, visit, baseline value-by-visit, treatment-by-visit, treatment-by-starting dose, starting dose-by-visit, and treatment-by-starting dose-by-visit interactions as fixed factors. Starting dose comparison combining ixekizumab Q2W and Q4W treatment regimens will be based on MMRM model with starting dose, baseline value, visit, baseline value-by-visit, and starting dose-by-visit interaction as fixed factors. The differences in response rates and LS mean changes between starting doses and the corresponding 95% CI will be reported as well.

Time to onset analyses will focus on earlier time points (for example, Weeks 1, 2, 4, and so on) for abovementioned response variables in a similar fashion. For time to first clinical response analysis, starting dose comparisons within and across ixekizumab Q2W and Q4W treatment regimens will be based on log-rank test.

For variables that are not collected at each postbaseline visit, data may exist at visits where the variable was not scheduled to be collected, due to early discontinuation visits. In these situations, data from the early discontinuation visit that do not correspond to the planned collection schedule will be excluded from the MMRM and categorical MMRM analyses (Andersen and Millen 2013). However, the data will still be used in other analyses, including shift analyses, change from baseline to last-observation carried forward (LOCF) or modified baseline observation carried forward (mBOCF) endpoint analyses, and other categorical analyses.

For selective efficacy measures, percent improvement will be calculated as $100 \times (\text{baseline score} - \text{observed scores}) / \text{baseline score}$, unless specified otherwise. If a patient has experienced an improvement, this measure will be positive. If a patient has experienced a worsening, this measure will be negative.

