6.3.1. Nonresponder Imputation

Analysis of categorical efficacy and health outcome variables will be assessed using a nonresponder imputation (NRI) method. Patients will be considered nonresponders for the NRI analysis if they do not meet the clinical response criteria or have missing clinical response data at the primary analysis time point. All nonresponders at Week 16 (Visit 8), as well as all patients who discontinue study treatment at any time prior to Week 16 for any reason, will be defined as nonresponders for the NRI analysis at Week 16. Randomized patients without at least 1 postbaseline observation will also be defined as nonresponders for the NRI analysis.

The NRI may be applied at any time point specified for analysis.

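### The starting-dose models leave out region, CRP status and, when pooled, regimen without a stated reason, costing the pooled 160 mg versus 80 mg logistic comparison about 2 to 6 points of power if CRP predicts response

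*SAP*

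**What the plan says.** Protocol 9.2.1 and SAP 6.1.1 set the same default: unless a section specifies otherwise, "the statistical analysis models will adjust for geographic region and baseline CRP status". Randomisation is stratified by country and CRP status (Protocol 6.2, SAP 5.2). Protocol 4.3 justifies CRP as a stratification factor because it has been reported to predict response in patients treated with TNF inhibitors. On starting dose, SAP 5.1 states: "Patients randomized to an ixekizumab regimen will be randomized to a 160 mg starting dose or 80 mg starting dose at a 1:1 ratio". This split is made separately for Q2W and Q4W.

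SAP 6.1.1 then specifies the starting-dose analyses as follows:

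- **Response rates, within regimen:** logistic regression with regimen, starting dose and their interaction.
- **Response rates, regimens pooled:** the comparison "will be based on logistic regression model with only starting dose in the model".
- **Mean change, within regimen:** an MMRM with regimen, starting dose, baseline value, visit and interactions.
- **Mean change, regimens pooled:** an MMRM with starting dose, baseline value, visit, and the interactions of visit with baseline value and with starting dose.
- **Time to first response:** a log-rank test, with no stratified version named.

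None of the four models contains region or CRP status, and neither pooled model contains regimen. Protocol 9.2.1 leaves the details of this analysis to the SAP.

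**The concern.** Exploring the effect of starting dose is listed among the other secondary objectives (Protocol Section 3, SAP Section 4). It rests on about 160 ixekizumab patients. CRP status and region are already collected and already used in the main efficacy models, and starting dose was randomised within regimen. Leaving these terms out gives up whatever prognostic information they carry, in a comparison with little power to spare.

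Two details in SAP 6.1.1 sharpen the contrast. Treatment-group comparisons of time to response get a second log-rank test stratified by region and CRP status; the starting-dose comparison does not. For CRP as an endpoint, the treatment-group MMRM uses region and CRP status and leaves out baseline value. The starting-dose MMRM does the reverse, although CRP is one of its named endpoints.

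**Working it through.** **1. The plan's own figure.** SAP 5.3 states: "With 80 patients per treatment group, this study will have approximately 96% power to test the superiority of ixekizumab Q2W to placebo", with "44% for ixekizumab 80 mg Q2W treatment group and 16% for the placebo group". It adds: "A 2-sided Fisher's exact test at the 0.05 level is assumed". Exact power is the sum, over all pairs (x1, x2), of Bin(x1; 80, 0.44) × Bin(x2; 80, 0.16) where Fisher's two-sided p ≤ 0.05. This gives 96.7%, which agrees with about 96%. The documents give no power for starting dose.

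**2. Group sizes.** SAP 5.3: "Approximately 320 patients will be randomized at a 1:1:1:1 ratio". So 320/4 = 80 per arm, 80/2 = 40 per starting dose within a regimen, and 2 × 40 = 80 per starting dose when pooled. No dropout inflation is stated. Under SAP 6.3.1 "all patients who discontinue study treatment at any time prior to Week 16 for any reason, will be defined as nonresponders" at Week 16, so everyone randomised stays in the denominator.

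**3. Unadjusted power.** Power = Φ{[d − 1.96·√(2·p(1−p)/n)] / √([p1(1−p1) + p2(1−p2)]/n)}, with p = 0.44 taken as the average response rate (an assumption, borrowed from the Q2W rate). For d = 0.20 (54% versus 34%):

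- n = 80: (0.200 − 1.96 × 0.0785)/0.0769 = 0.60, so power is 72.6%.
- n = 40: (0.200 − 1.96 × 0.1110)/0.1087 = −0.16, so power is 43.6%.

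For differences of 10, 15 and 22 points, power is 24.5%, 48.0% and 80.6% pooled, and 14.4%, 26.9% and 50.9% within one regimen.

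**4. Pooled logistic model, with and without the omitted terms.** This used 20,000 simulated trials per scenario, 40 patients in each regimen-by-starting-dose cell, and the Wald test at two-sided 0.05. Assumptions not in the documents are the starting-dose differences, 55% elevated CRP, 50% in Europe, and all covariate odds ratios. Simulation standard error is at most about 0.35 point. For a 20-point difference:

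| CRP / region / regimen OR | Dose only | With CRP, region, regimen | Gain (points) |
|---|---|---|---|
| 1 / 1 / 1 | 72.1% | 72.9% | 0.8 |
| 2 / 1 / 1 | 71.6% | 73.4% | 1.8 |
| 2 / 1.5 / 1.25 | 71.9% | 74.5% | 2.6 |
| 3 / 1.5 / 1.25 | 72.1% | 75.9% | 3.8 |
| 4 / 2 / 1.5 | 71.7% | 77.9% | 6.2 |

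At 15 and 22 points the gains with CRP prognostic run from 1.6 to 6.2 points. The largest gains also assume region and regimen effects. Null rejection is 4.4 to 4.8% for dose only and 4.9 to 5.2% adjusted. Adjustment therefore does not materially inflate type I error, and the gain of about 1 point with nothing prognostic probably reflects a slightly conservative unadjusted Wald test.

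**5. Regimen alone.** Adding only regimen changes pooled power by at most 0.5 point.

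**6. Within-regimen logistic model.** Adding CRP status and region for a 20-point difference moves power from 46.0% to 44.3% with nothing prognostic, from 45.2% to 44.5% at CRP OR 2 alone, and from 44.7% to 48.0% in the strongest scenario. Across all differences tried, the change is about −2 to +4 points, with clear gains only at a CRP odds ratio of 3 or more.

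**7. MMRM.** If the omitted terms explain a further share R² of residual variance, the standardised effect is divided by √(1 − R²). From 80% power the starting value is 1.960 + 0.842 = 2.802. At R² = 0.05, 2.802/√0.95 = 2.874, and Φ(2.874 − 1.960) = 82.0%. At R² of 0.02 and 0.10, power is 80.8% and 84.0%.

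**8. Source of the logistic gain.** In a separate simulation (4,000 trials; 20-point difference; CRP OR 3, region 1.5, regimen 1.25), the mean standard error of the log odds ratio rises from 0.328 to 0.351 on adjustment, a factor of 1.07. Power still increases because the conditional log odds ratio grows by more than that.

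**The case against.** The default carries an explicit exception, SAP 6.1.1 uses it, and Protocol 9.2.1 delegates the choice. The objective is only to explore. It has no power target, it has no multiplicity control (SAP 6.10.4), and differences are reported with 95% confidence intervals. All of that stands: this is an unexplained departure from a default, not a contradiction.

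A reader might infer that these are the only models without the covariates. They are not. The efficacy and safety subgroup models (SAP 6.14.1, 6.14.2), the anti-drug-antibody efficacy model (6.12.8.2.2) and the laboratory and vital-sign ANCOVAs (6.1.1) omit them too.

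A reader might also infer that leaving out regimen biases the pooled comparison. It does not, because starting dose is allocated 1:1 within each regimen. Nor does adjustment shrink the standard error in a logistic model (step 8). The MMRMs already keep baseline value, which leaves less for CRP status to explain.

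The size rests on assumptions. CRP as a predictor is documented only under TNF inhibitors, with no effect size. At a 10-point difference, a simulation of 4,000 trials per scenario gives a gain of about 2 points (24.8% to 26.6% at CRP OR 2), against 1.2 points (23.3% to 24.5%) with nothing prognostic.

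Finally, SAP Version 3 was approved after unblinding (SAP Section 3). One might suspect that the models were chosen with results in view. The revision history lists no change to the Period 2 section after Version 2, which was approved before unblinding, so the documents do not support that suspicion. The date does limit how an added analysis may be labelled.

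**Conclusion.** The point is real but minor. The omissions are as described, and the available text gives no reason for them. In the pooled logistic comparison they cost about 2 to 6 points of power if elevated CRP has an odds ratio of 2 to 4 for response to ixekizumab, with the top of that range also assuming region and regimen effects. They cost about 1 point if no covariate is prognostic. CRP status accounts for most of the gain.

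The documents do not support extending the power claim to the within-regimen logistic comparisons, where adjustment can lose as well as gain. With about 40 per group and roughly 44% power for a 20-point difference, sample size is the limit there, and covariates do not repair it. Primary and major secondary inference is unaffected.

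**What to change.** - Add region, baseline CRP status and regimen to the pooled starting-dose logistic model and pooled MMRM.
- Add region and CRP status to the within-regimen models, for consistency with the default rather than for power.
- For the CRP endpoint, follow the covariate set that SAP 6.1.1 gives for treatment comparisons: region and CRP status, without baseline value.
- Add the log-rank test stratified by region and CRP status that is already used for treatment comparisons.
- If the simpler models are kept alone, state why.

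The cost is SAP wording and a few model terms on data already collected. The logistic odds ratio becomes conditional on the covariates, so the response-rate difference and its 95% confidence interval should still be reported. Because Version 3 follows unblinding, the models as written should stand and the adjusted results should be labelled supplementary.

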6.1.2. General Considerations for Analyses during the Extended Treatment Period (Period 3)

Unless otherwise specified, Period 3 starts at the first injection of study treatment at Week 16 (Visit 8) and ends on the date of Week 52 (Visit 15) or the ETV (between Weeks 16 and 52).

For the efficacy and health outcome analyses, baseline is defined as the last available value before the first injection in Period 2 and, in most cases, will be the value recorded at Week 0 (Visit 2).

Unless otherwise specified, for the safety analyses during Period 3, baseline is defined as the last available value before first injection of ixekizumab in Period 3. In most cases, this will be the measure recorded at Week 16 (Visit 8). For adalimumab patients in Period 2 who are randomized to ixekizumab during Period 3, this will be the measure recorded at Week 20 (Visit 9). For treatment-emergent adverse events (TEAEs), baseline is the events ongoing just prior to the first injection of the study drug injection at Week 16 (for placebo and ixekizumab patients) or Week 20 (for adalimumab patients who are randomized to ixekizumab during Period 3).

The number and percentage of patients having categorical efficacy response (for example, ASAS40) will be summarized by treatment group for all scheduled visits (NRI), including Week 52 (Visit 15) during Period 3.

In addition, the number and percentage of patients achieving response on ASAS20 for those who did not achieve response at Week 16, and the number and percentage of patients maintaining response for those who achieved response at Week 16, will be summarized by treatment group for all scheduled visits (NRI), including Week 52 (Visit 15) during Period 3. Similar summary will be provided for ASAS40.

Each continuous efficacy and health outcome score and change from baseline (or percent improvement) will be summarized by treatment group at all scheduled visits, including Week 52 (Visit 15) using descriptive statistics (n, mean, SD, median, minimum and maximum). Missing data will be imputed using mBOCF method (Section 6.3.2).

The categorical safety measures will be summarized with incidence rates. The mean change of the continuous safety measures will be summarized at all scheduled visits.

6.1.3. General Considerations for Analyses during Combined Blinded Treatment Dosing Period and Extended Treatment Period (Combined Periods 2 and 3)

Selective efficacy and health outcome analyses will be performed for Combined Periods 2 and 3 for ITT Population who are randomized to ixekizumab at Week 0 (Visit 2). These analyses included the primary endpoint, all major secondary endpoints, as well as ASDAS<2.1, ASDAS clinically important improvement and major improvement, and MRI SIJ SPARCC score.

Unless otherwise specified, Combined Periods 2 and 3 starts at the first injection of study treatment at Week 0 (Visit 2) and ends on the date of Week 52 (Visit 15) or the ETV (between Weeks 0 and 52).

For the efficacy and health outcome analyses, baseline is defined as the last available value before the first injection in Period 2 and, in most cases, will be the value recorded at Week 0 (Visit 2). For efficacy measures, if the patient does not take any injection, the last available value on or prior to randomization date will be used.

The number and percentage of patients achieving a categorical response (for example ASAS40) will be summarized by treatment group for all scheduled visits (NRI), including Week 52 (Visit 15).

Continuous measure and change from baseline will be summarized by treatment group at all scheduled visits, including Week 52 (Visit 15) using descriptive statistics (n, mean, SD, median, minimum and maximum). Missing data will be imputed using mBOCF method (Section 6.3.2).

Selective safety analyses will be performed for Combined Periods 2 and 3 for the Safety Population who are randomized to ixekizumab at Week 0 (Visit 2).

For above safety analyses, baseline will be defined as the last available value before the first injection at Week 0. In most cases, this will be the measure recorded at Week 0 (Visit 2). For TEAEs, baseline is defined as the time from Visit 1 to the date/time of the first injection.

Additional categorical safety analyses will be conducted in the All Ixekizumab Exposures Safety Population (defined in Section 6.1.5.), for each patient, only periods in which ixekizumab is administered are included. Exposure-adjusted incidence rates of AE during Week 0-52 will be provided. For these safety analyses, baseline is defined as below:

- If ixekizumab is dispensed at Week 0, baseline will be defined as the last available value before the first injection at Week 0. In most cases, this will be the measure recorded at Week 0 (Visit 2). For TEAEs, baseline is defined as the time from Visit 1 to the date/time of the first injection.
- If adalimumab is dispensed at Week 0, then the baseline is the last non-missing value up to the visit (V9) that the patient first receives an injection of ixekizumab.
- If placebo is dispensed at Week 0, then the baseline is the last non-missing value up to the visit (V8) that the patient first receives an injection of ixekizumab.

6.1.4. General Considerations for Analyses during the Post-Treatment Follow-Up Period (Period 4)

For the safety analyses during Period 4, baseline is defined as the last non-missing assessment on or prior to entering Period 4, that is, on or prior to Week 52 (Visit 15), or ETV.

Safety data collected will be summarized using descriptive statistics.

Efficacy data collected during Period 4 will be summarized as described in Section 6.10.5.

